Four modules were offered during the next 18 months (phase 2): “Healthy and Fit,” which combined healthy eating patterns and regular exercise to avoid weight gain during the holiday season; “Step Challenge,” which was a team-based module, focusing on increasing physical activity by using a fitness device to track steps; and two consecutive “Nutrition for a Lifetime” modules, which were designed to help employees achieve and maintain a healthy lifestyle by combining healthy nutrition, exercise, stress management and sleep patterns. In addition, participants had the opportunity to log their step counts using a wearable device and this information was gathered between January 2017 and July 2017. Please refer to Appendix 1 for detailed information on the components of the wellness program by module, including requirements and incentives. Employees had opportunities to receive incentive payments through completion of the PHA and the biometric screenings, in addition to participation in the individual modules of the program.

In each treatment worksite, a Registered Dietitian employed by Wellness Workdays coordinated and led the wellness programming. The Registered Dietitians engaged employees in the wellness program modules, educated them about the content of the program, and led employees in various creative activities such as group fitness and cooking demonstrations. Each Registered Dietitian had the flexibility to tailor the day-to-day programming around the themes of the modules. The Registered Dietitians spent approximately 8 hours per week at each worksite.

III. Randomization

The wellness program was implemented in a randomly selected subset of BJ’s Wholesale Clubs. Each club is a standalone worksite, with an average of 118 employees at any given time. At the beginning of the study, there were 201 BJ’s worksites in the U.S. along the East coast, extending from Maine to Florida. We eliminated 41 worksites because they were geographically remote or had employee pools with substantially different insurance coverage from the others, leaving 160 worksites in our sample.

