Among these worksites, we randomly selected 25 “treatment” worksites that would receive the wellness program and 25 “primary control” worksites for phase 2.⁵ These primary control worksites participated in data collection through PHAs and in-person biometric screenings, but did not receive the wellness program treatment. **Figure 1** shows the locations of the 25 treatment and 25 control worksites across the Eastern U.S. The remaining 110 worksites served as “secondary controls.” which were included in analyses of administrative data. Thus, the primary data described below was collected from the 50 treatment and primary control worksites; administrative data were compiled for all 160 worksites. **Figure 2** shows a Consolidated Standards of Reporting Trials (CONSORT) flow diagram for our phase 2 evaluation, including the sample sizes of treatment and control groups.

⁵ For the first 18 months of the study (phase 1), there were 20 treatment and 20 primary control sites.

Randomization at the worksite level allows us to assess the effects of interventions that aim to affect workplace culture or operate on a group level, such as using common break rooms to stage nutrition demonstrations, team-based activities, or worksite level prizes.

IV. Data

Our analysis focuses on outcomes from five data categories. The Table below displays the source of each data set and the study population from which it is derived.

Summary of the Components of Data Collected				
Data	Source	Treatment Worksites (25)	Primary Control Worksites (25)	Secondary Control Worksites (110)
Administrative Data				
Employment records	BJ's	All employees	All employees	All employees
Claims data (medical and pharmaceutical)	Cigna (via BJ's)	Employees insured by Cigna	Employees insured by Cigna	Employees insured by Cigna
Primary Data				
Biometric screening data	Wellness Workdays	Employees completing screening	Employees completing screening	None (by design)
Personal Health Assessment	Wellness Workdays	Employees completing survey	Employees completing survey	None (by design)
Participation in the treatment	Wellness Workdays	All employees	None (by design)	None (by design)

A. Administrative Data

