In this representative estimating equation, Y_{ijt} denotes an outcome of interest, such as medical spending, for individual i who is employed in worksite j at time t . $TREATMENT_{jt}$ is a binary indicator of whether the individual's worksite was randomized into treatment or control. We assigned each individual to the worksite at which he or she was employed when the treatment began in January 2015. $TIME_WORKED_{ijt}$ is the share of total available work hours in the study period that the individual actually worked; it is expressed in percentage terms. The effect of randomization to a treatment worksite is allowed to vary based on exposure to the treatment (measured via time worked during the treatment period). The treatment effect is captured by $\beta_1 + \beta_3 * Exposure$. The average effect of randomization into the treatment group can be summarized by assessing this at the average level of exposure. While we will produce estimates of the average effect of randomization into treatment, as captured in the layout of Tables 3-6, we will additionally show results for both β_1 and β_3 for each of our results in a set of parallel tables.

X_{ijt} represents a vector of covariates that may help improve precision as well as account for chance differences in characteristics between treatment and control groups, including:

- Age indicators: <20 years (omitted), 20-29, 30-39, 40-49, 50-59, and 60 and greater.
- Sex indicator: male (omitted), female
- Age-sex interactions
- Race: white (omitted), black, Hispanic, and other
- Employment characteristics (measured at baseline for the stably employed subsample):
 - Part-time (omitted), full-time
 - Salaried (omitted), hourly
 - Sales worker (omitted), non-sales worker, and other worker.

ε_{ijt} is the idiosyncratic error term. The models are weighted using the sample weights described above. Standard errors were clustered at the worksite level.

B. Local average treatment effect (LATE)

While our ITT analysis explores the effect of being randomized into a treatment worksite, a related but distinct question is: what is the effect of participating in the wellness program on the outcomes of interest? The answer to this second question will be different if not all employees in treatment worksites elect to participate. Because the choice to participate in the program is endogenous, simply including participation as a right-hand side variable may produce biased

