We will analyze how the effect of the wellness program varies along 3 pre-specified dimensions: age (less than 40 years or 40 and above), sex (male or female), and employment status (full-time vs. part-time). In our model, these subgroup analyses are implemented using a set of two-way interaction terms and a triple interaction term. Equation 5 below shows these interaction terms in our ITT framework, using the subgroup analysis on age as the representative equation, where $age40_{it}$ is defined as 1 if the individual is age 40 years or older, and 0 otherwise.

$$\begin{aligned}
 Y_{ijt} = & \beta_0 + \beta_1 TREATMENT_{jt} + \beta_2 TIME_WORKED_{ijt} + \beta_3 Age40_{it} \\
 & + \beta_4 TREATMENT_{jt} * TIME_WORKED_{ijt} + \beta_5 TREATMENT_{jt} * Age40_{it} \\
 & + \beta_6 TIME_WORKED_{ijt} * Age40_{it} + \beta_7 TREATMENT_{jt} * TIME_WORKED_{ijt} * Age40_{it} \\
 & + \rho X_{ijt} + \varepsilon_{ijt}
 \end{aligned} \tag{5}$$

In this model, the coefficient on the triple interaction term, β_7 , represents the marginal effect of an additional unit of exposure (as measured by time worked) among employees 40 years or older who were randomized into treatment. For those under age 40, the effect of the wellness program is represented by $\beta_1 + \beta_4 * Exposure$. For those over age 40, the effect of the wellness program is represented by $\beta_1 + \beta_4 * Exposure + \beta_5 + \beta_7 * Exposure$, or $(\beta_1 + \beta_5) + (\beta_4 + \beta_7) * Exposure$. The average effects for each group can be derived by evaluating this at the average level of exposure. We will evaluate whether any differences are statistically significant.

E. Worksite-level analyses

We complement our analyses at the individual level with analyses at the worksite level. Worksite-level data were generated by aggregating values for individuals up to their initial worksite. This aggregation was weighted by the number of hours each employee worked during the treatment period. The estimating equation below captures the framework of the worksite-level analyses.

$$Y_{kt} = \beta_0 + \beta_1 TREATMENT_{kt} + \beta_2 X_{kt} + \varepsilon_{kt} \tag{6}$$

In equation (6), the subscript k denotes a worksite. Analogous to the individual-level analyses, Y_{kt} represents an outcome for worksite k at time t . $TREATMENT_{kt}$ is a binary indicator of

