randomization into treatment or control, with β_1 indicating the average worksite-level effect of being randomized into treatment. The vector of covariates X_{kt} comprises the same set of observable characteristics for individuals, aggregated to the worksite level using weighted averages (generating percentages for binary variables). The worksite-level regressions are weighted by worksite size, as measured by the total hours worked by all employees at a worksite, with standard errors adjusted for heteroscedasticity. For estimates of program effect that are significant in the individual-level analysis, we will produce parallel LATE estimates at the workplace level, analogously using treatment status as an instrument for participation.

Although the employees at each worksite could change over time, the worksites themselves were all stably represented in our data. However, at the 18-month mark, 5 worksites previously in the control group entered the treatment group. In our base specification, we will assess effects for the 20 worksites that were continuously treated throughout the 3-year period (omitting the additional 5 from the analysis altogether). As an alternative specification, we will also evaluate effects at the worksite level when considering the 5 additional worksites in the treatment group.

F. Sensitivity analyses

We conduct several types of sensitivity analyses. First, in the statistical analyses above, our base regression models use linear regression even for binary outcomes. The OLS estimator has been shown to perform better than other non-linear approaches in estimating the average population effect, particularly with large samples.¹⁰ However, OLS also has limitations, such as its sensitivity to outliers. To test the robustness of our main results to changes in functional form, we will fit logit models for binary outcome variables.

Second, we will present LATE results with alternative definitions of participation. As defined above, these include a binary indicator of participation based on completing at least one module, and a high participation indicator defined as completing at least 3 modules.

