Notes: Table reports the coefficient on TREATMENT from estimating equation (1) by OLS (column 2), and the coefficient on PARTICIPATION from estimating equation (2) by IV (column 3). Standard errors are listed in parentheses. Column 1 reports the mean of each employment outcome in the control group for each sample (with standard deviation in parentheses, followed by the number of observations for each outcome). All regressions will include demographic and employment controls (age, sex, age-sex interactions, race/ethnicity, Cigna coverage status, full-time status, paid hourly status, and job category) and cluster standard errors at the worksite (for employee-level regressions). Employee-level and stably employed subsample control means are weighted by a weight that balances treatment and control on demographic characteristics. Worksite-level control means are not traditionally weighted: individual-level records are collapsed at the worksite-level and weighted by the total number of hours worked at each worksite. For worksite level results on tenure, the outcome was defined as the percent of total days at the worksite during the study period that was worked by employees at the worksite.

§ Tenure was defined as the number of days worked during the treatment period for the employee-level mean and stably employed subsample mean; it was defined as the percent of the entire treatment period worked by employees in the worksite-level mean.

Table 4: Impact on Medical & Pharmaceutical Spending and Utilization

	Employee-level			Stably Employed Subsample			Worksite-level (per 2000 work hours)		
	Mean in Control Group (1)	Reduced Form (Linear) (2)	2SLS (Linear) (3)	Mean in Control Group (1)	Reduced Form (Linear) (2)	2SLS (Linear) (3)	Mean in Control Group (1)	Reduced Form (Linear) (2)	2SLS (Linear) (3)
Medical Spending									
Total Spending	4800.57 (18559.82)			4721.85 (19056.92)			5044.74 (2994.54)		
Medical Utilization									
Number of Office visits	3.90 (4.47)			3.95 (4.33)			4.21 (0.93)		
Number of Hospitalizations	0.09 (0.40)			0.08 (0.36)			0.08 (0.05)		
Number of ER Visits	0.28 (0.75)			0.26 (0.61)			0.27 (0.11)		
Pharmaceutical Spending									
Total Spending	1237.60 (6921.32)			1227.32 (7115.67)			1317.72 (1145.17)		
Pharmaceutical Utilization									
Number of Distinct Medications	5.49 (6.44)			5.91 (6.54)			6.00 (1.30)		
Total Medication Months	11.20 (19.31)			11.41 (19.37)			12.39 (4.38)		
N	7,174			5,779			135		

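### For spending compared across 25 (or 20) treated and 135 control worksites, the unspecified robust standard errors make a chance saving about two to three times as likely as the nominal 2.5%

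*Combined protocol and SAP*

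**What the plan says.** Section VI.A fits equation (1) by linear regression with balance weights and states "Standard errors were clustered at the worksite level". Section VI.E fits equation (6) to worksite aggregates "with standard errors adjusted for heteroscedasticity". Neither section names a robust variance variant, a reference distribution, degrees of freedom, a bootstrap or a randomization test. No significance level is given; section VI.D says only "We will evaluate whether any differences are statistically significant".

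On the number of sites, section III excludes 41 of 201 clubs, "leaving 160 worksites in our sample": 25 treated, 25 primary controls and 110 secondary controls. Tables 3 and 4 use both kinds of control (41,376 employees; 7,174 insured), so administrative outcomes compare 25 sites with 135. In the base worksite-level model, "we will assess effects for the 20 worksites that were continuously treated throughout the 3-year period", and the 5 added treated sites are dropped. That leaves 20 against 135.

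Section VI.F acknowledges that OLS is sensitive to outliers. Its only functional-form check is a logit model for binary outcomes, so no planned check addresses skewed spending.

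**The concern.** The precision of a 25 v 135 comparison is governed by the 25. Robust standard errors estimate the treated arm's variance from 20-25 site totals, but the usual correction and degrees of freedom count all 155-160 sites.

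Skewness adds a problem of direction. If the treated sites happen to draw few very expensive patients, their mean is low and so is their estimated variance. The t-statistic is then pushed far into the savings tail. A chance excess of expensive patients raises the mean and the standard error together, which mutes the statistic. With equal arms the two effects largely cancel; at 25 v 135 they do not.

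Whether wellness programs reduce health care spending is a central question of this trial, and this test errs towards finding that they do.

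**Working it through.** The plan states no error rate or power figure, so there is none to reproduce.

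**Inputs from the documents**
- Medical spending, employee level (Table 4): 18559.82/4800.57 = 3.87 (SD/mean).
- Pharmaceutical spending, employee level (Table 4): 6921.32/1237.60 = 5.59.
- Insured employees: 7,174 + 1,385 = 8,559 (agrees with Table 10); 8,559/160 = 53.5 per site.
- Spread of site size (Figure 2): 88/304 = 0.29.
- Covariates (section VI.A): 5 age + 1 sex + 5 age-sex + 3 race + 1 full-time + 1 hourly + 2 job type = 18.

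**Assumptions:** two-sided 5%; CR1 (employee) or HC1 (worksite) errors with a t reference; spending gamma or lognormal, matched to the Table 4 mean and SD.

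**Step 1: symmetric outcomes, analytically (equal site sizes).** Treated sites contribute (1/25)/(1/25 + 1/135) = 84% of the variance, or 87% with 20 sites. The Satterthwaite degrees of freedom are

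(1/a + 1/b)² / [(1/a)²/(a−1) + (1/b)²/(b−1)],

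which gives 33.5 for 25 v 135 and 25.0 for 20 v 135, against 159 and 154 from counting all sites. The CR1 standard error is 0.985 (0.981) of the unbiased one. The effective critical value is therefore 1.975 × 0.985 = 1.95 (1.94 for 20 sites), and the two-sided size is 6.0% (6.4%). The inflation is mild.

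**Step 2: skewed spending, by simulation with no effect.** Percent of runs; nominal is 2.5 in each tail.

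| Setting | False saving | False increase |
|---|---|---|
| Employee, medical, gamma, 25 v 135 | 4.4-5.0 | 1.9-2.1 |
| Employee, medical, lognormal, 25 v 135 | 5.9-6.6 | 1.0-1.2 |
| Equation (1) with covariates and weights, lognormal, 25 v 135 | 7.1 | 1.1 |
| Employee, pharmaceutical, lognormal, 25 v 135 | 7.5 | 0.7 |
| Employee, medical, gamma, 20 v 135 | 5.1-5.3 | 1.8-1.9 |
| Employee, medical, lognormal, 20 v 135 | 7.1-7.8 | about 1 |
| Worksite, HC1, lognormal, 20 v 135, 0 / 18 covariates | 6.2 / 5.2 | 1.4 / 1.9 |
| Worksite, HC1, lognormal, 25 v 135, 0 / 18 covariates | 5.9 / 4.4 | 1.3 / 1.8 |

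Ranges cover repeated runs. With 4,000 replicates, the Monte Carlo error on a 6% tail is √(0.06 × 0.94/4,000) = 0.4 points. Total two-sided error across these settings is 6.2-8.7%. The plan specifies 20 treated sites only for the worksite-level base model, so the 20 v 135 employee rows show sensitivity.

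The Table 4 worksite SD implies a small intraclass correlation: 18559.82/√53.14 = 2,546 expected with no clustering, against 2,994.54, or about 0.007. (The two columns are scaled differently, so this is rough.) Adding 0.007 left the lognormal tails at 6.1% and 1.1%.

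**Step 3: comparisons without the problem.** Symmetric outcomes simulated at 20 or 25 v 135 give 5.6-6.8% two-sided, consistent with step 1. At 25 v 25, two-sided size is 5.3% (normal), 4.9% (gamma) and 4.2% (lognormal).

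**Step 4: remedies.** A CR2-type error with Satterthwaite degrees of freedom corrects normal outcomes (4.7-5.2%) but leaves the savings tail at 4.1-4.3% (gamma) and 5.2-6.0% (lognormal). Permuting worksites and recomputing the studentised difference gives a savings tail of 2.1-2.8% and a two-sided size of 4.6-5.2% in every 20 v 135 and 25 v 135 setting, skewed or not.

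**The case against.** The strongest reply is that the plan names no variance variant, so nobody can say that the planned errors are wrong by a given amount. That is fair. The figures describe conventional defaults, and what the documents establish is that no small-sample method is specified. The variant does matter: HC3 in the worksite model with 18 covariates brings the lognormal savings tail down to 3.0-3.5%, though it stays at 5.6% without covariates. The reply limits the precision of the claim but does not remove the gap.

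The size also depends on an assumed distribution, since Table 4 gives only a mean and an SD. This stands too, and it is why gamma and lognormal results are both shown. The direction is the same for both.

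Three stronger readings are tempting and do not hold.
- A reader might infer that every interval in the plan is too narrow. Tables 5-6 compare 25 with 25 sites, and step 3 finds essentially no inflation there.
- A reader might take a doubled error rate to mean that a 5% test runs at 10% or more. The doubling is in one tail, against 2.5%; the other tail shrinks, and the total is about 6-9%.
- A reader might blame 18 covariates for using up 20 treated sites. Equation (6) fits common slopes across about 155 sites, and adding the covariates lowered the savings tail.

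**Conclusion.** The point holds for administrative outcomes, and it matters mainly for medical and pharmaceutical spending. Under the stated assumptions a chance saving is roughly 1.8 to 3.1 times as likely as the nominal 2.5%, and at least twice as likely as a chance increase. The cause is skewed spending combined with unequal numbers of sites; standard errors that are generally too small are not the main reason. Absenteeism, tenure and similar Table 3 outcomes would be only mildly affected if they are roughly symmetric, and biometric and survey outcomes are not affected. The change should be made because spending is a headline outcome and no planned sensitivity analysis would reveal the problem.

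**What to change.** For Tables 3-4, and above all for the two spending outcomes, take ITT p-values and intervals from a worksite-level randomization test.

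1. Use the studentised ITT estimate at average exposure, β1 + β3 × mean exposure, as the statistic; for equation (6), use the studentised β1.
2. Re-draw assignment as it was actually made. Sections III and VI.F indicate 20 + 20 sites and then 5 + 5 from former secondary controls, but not how the later sites were chosen. The sponsor must supply that procedure. The simulated permutations in step 4 shuffled all sites in one stage.
3. Rebuild the section V.B balance weights in each draw, because they depend on the assignment.
4. Obtain intervals by inverting the test.
5. Keep clustered or robust errors as descriptive and name the variant. Do not rely on CR2 with Satterthwaite degrees of freedom alone for spending.
6. For 2SLS, carry over the ITT permutation p-value only in the just-identified model (equations 7-9). Equations (3)-(4) use both TREATMENT and its interaction with TIME_WORKED as instruments, so permute a joint Anderson-Rubin statistic on the two terms.
7. State the significance level and sidedness.

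The cost is SAP wording, computing time, and somewhat wider or asymmetric intervals. Tables 5-6 need no change on this account.

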Analyses are conducted at the individual employee level and at the worksite level. The treatment period in our phase 2 analysis is defined as the 36-month period spanning January 2015 through December 2017. (In comparison, the phase 1 analysis spanned January 2015 through mid-2016).

A. Intention-to-treat analysis

In the individual-level intention-to-treat (ITT) analysis, our goal is to estimate the average effect of a worker being randomized into a treatment worksite on outcomes of interest. Given that the

⁹ Zubizarreta JR. Stable weights that balance covariates for estimation with incomplete outcome data. *Journal of the American Statistical Association*. 2015 Sep;110(511):910-922; Wang X, Zubizarreta JR. Minimal approximately balancing weights: Asymptotic properties and practical considerations. *Biometrika*. 2017;103(1):1-22; Hirshberg DA, Zubizarreta JR. On two approaches to weighting in causal inference. *Epidemiology*. 2017;28(6):812-816.

treatment is implemented at the worksite level and that there are likely fixed costs of the program, the ITT estimates (and the worksite level analysis) are informative.

We use a base specification that includes a dose-response measure of the effect of exposure to the intervention (as measured by time worked). This specification captures the overall effect of randomization into treatment as well as how the effect of randomization to a treatment site varies with additional exposure to the treatment.

$$Y_{ijt} = \beta_0 + \beta_1 TREATMENT_{jt} + \beta_2 TIME_WORKED_{ijt} + \beta_3 TREATMENT_{jt} * TIME_WORKED_{ijt} + \beta_4 X_{ijt} + \varepsilon_{ijt} \quad (1)$$

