estimates of the effect of the treatment. Therefore, we model the impact of participation on outcomes using a two-stage least squares (2SLS) specification:

$$Y_{ijt} = \gamma_0 + \gamma_1 PARTICIPATION_{ijt} + \gamma_2 X_{ijt} + \mu_{ijt} \quad (3)$$

Where the endogenous *PARTICIPATION* variable is estimated via the first stage regression:

$$PARTICIPATION_{ijt} = \pi_0 + \pi_1 TREATMENT_{jt} + \pi_2 TIME_WORKED_{ijt} + \pi_3 TREATMENT_{jt} * TIME_WORKED_{ijt} + \pi_4 X_{ijt} + v_{ijt} \quad (4)$$

We include the exposure interaction in the first stage, parallel to our ITT estimates. The coefficient γ_1 in equation (3) identifies the effect of participation on outcomes.

On the left-hand side of the first stage, this base specification uses the continuous definition of participation, with values from 0-12, which indicates the number of modules an individual participated in during the 36-month study period. **Table 10** shows the results of first stage estimates for this and for our alternative definitions of participation (including indicators for completion of 3 or more modules of the program or completion of at least 1 module of the program). In robustness specifications, we use these alternative definitions of participation.

If no one in the control group receives the treatment, we can interpret the 2SLS estimates of the LATE as a treatment on the treated (TOT). Empirically, we expected this to be essentially true by construction because the control worksites did not receive the wellness modules. However, because we assigned employees to worksites based on their initial locations of employment at the beginning of the study period, a small number of employees who moved from control worksites to treatment worksites during the intervention period did receive an opportunity to participate in the program. This explains the fact that the control group means in **Table 10** are nearly, but not exactly, zero.

C. Addressing endogeneity concerns

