The key identifying assumption is that the only mechanism through which being employed in a treatment worksite affects outcomes is through the availability of the wellness program. There are two threats to this assumption. First, to the extent that covariates were not balanced at baseline and those covariates affect the outcomes of interest, that imbalance could bias our estimates. We control for observed covariates and apply weights to balance covariates between treatment and control. Despite these adjustments, unobserved covariates might still be imbalanced.

Second, to the extent that the wellness program affected hiring or tenure of employees, their presence in the data set may be endogenously determined. We address the issue of endogenous entry by pre-specifying a subsample of those who were already employed at the time the intervention began. We defined this more restrictive “stable employment” subsample as comprising employees who had worked continuously for 13 weeks prior to the wellness program. This comes at a cost of reducing the overall sample size. Our goal in choosing the definition for this subsample was to balance the costs and benefits, as detailed in Appendix 2.

In this stably employed subsample, however, exit from the firm's workforce is still potentially endogenous. We deal with this concern in two ways. First, we will test balance on exit between treatment worksites vs. from control worksites overall and for subgroups. Indeed, tenure and time worked are among our primary outcomes. To the extent that we observe any unbalanced exit, we will perform a bounding exercise (assuming that those who exited have outcomes working against any observed effects of the intervention).

D. Subgroup analyses

We pre-specified three subgroup analyses. We selected these subgroups based on differences in key outcomes within the control group for those with different baseline characteristics, such as differences in medical spending by age or in reported exercise by sex (**Table 11**).

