Note: Control means and first stage estimates of the impact of TREATMENT on alternate definitions of PARTICIPATION. All regressions include demographic and employment controls (age, sex, age-sex interactions, race/ethnicity, full-time status, paid hourly status, and job category) and cluster standard errors at the worksite level. All samples other than the sample with Cigna coverage also include a control for whether or not the employee ever had Cigna coverage during the treatment period. Employee-level regressions are weighted by a weight that balances treatment and control on demographic characteristics. Standard errors shown in parenthesis and p-values in brackets.

Panel B: Employee-level—Stably Employed Sub-sample

	All		Surveyed		Cigna	
	(7) Control Mean	(8) Estimated First Stage	(9) Control Mean	(10) Estimated First Stage	(11) Control Means	(12) Estimated First Stage
Completed any module (%)	0.57	49.75 (2.82) [0.00]	3.90	79.22 (2.74) [0.00]	0.97	59.54 (3.24) [0.00]
Modules completed (#)	0.02	2.56 (0.21) [0.00]	0.15	5.41 (0.39) [0.00]	0.04	3.41 (0.29) [0.00]
3 or more modules (%)	0.35	35.04 (2.47) [0.00]	2.96	67.78 (3.39) [0.00]	0.61	45.79 (3.15) [0.00]
Average total incentive payment (\$)	0.75	97.62 (8.45) [0.00]	5.92	217.91 (15.74) [0.00]	1.54	163.36 (13.80) [0.00]
N	13,000	15,344	747	1,396	5,779	6,907

Note: Control means and first stage estimates of the impact of TREATMENT on alternate definitions of PARTICIPATION. All regressions include demographic and employment controls (age, sex, age-sex interactions, race/ethnicity, full-time status, paid hourly status, and job category) and cluster standard errors at the worksite level. All samples other than the sample with Cigna coverage also include a control for whether or not the employee ever had Cigna coverage during the treatment period. Employee-level regressions are weighted by a weight that balances treatment and control on demographic characteristics. Standard errors shown in parentheses and p-values in brackets.

Panel C: Worksite level

	All		Surveyed		Cigna	
	(1) Control Mean	(2) Estimated First Stage	(3) Control Mean	(4) Estimated First Stage	(5) Control Means	(6) Estimated First Stage
Completed any module (%)	0.22	28.19 (1.27) [0.00]	3.07	62.25 (1.89) [0.00]	0.91	57.29 (2.83) [0.00]
Modules completed (#)	0.01	1.17 (0.09) [0.00]	0.11	3.49 (0.22) [0.00]	0.03	3.18 (0.27) [0.00]
3 or more modules (%)	0.12	16.69 (1.12) [0.00]	2.27	46.65 (2.16) [0.00]	0.54	43.68 (2.76) [0.00]

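### The employee-level LATE puts hours worked in the first stage but leaves it out of the outcome equation, so outcomes that vary with hours get a biased participation effect

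*Combined protocol and SAP*

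**What the plan says.** Section VI.B of the combined protocol and SAP defines the employee-level LATE by two equations.

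- Outcome equation (3): Y on PARTICIPATION and X.
- First stage (4): PARTICIPATION on TREATMENT, TIME_WORKED, TREATMENT × TIME_WORKED and X.

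The only explanation is "We include the exposure interaction in the first stage, parallel to our ITT estimates". The ITT model, equation (1) in section VI.A, has TIME_WORKED as a term of its own beside X, as do equations (4) and (5). TIME_WORKED is the share of available hours over the study period that the person actually worked, so it is measured after randomization. Section VI.C adds: "Indeed, tenure and time worked are among our primary outcomes". The identifying assumption there concerns site assignment alone: "the only mechanism through which being employed in a treatment worksite affects outcomes is through the availability of the wellness program".

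The tables do not settle which model will be run. The notes to Tables 3–6 describe column 3 as "the coefficient on PARTICIPATION from estimating equation (2) by IV (column 3", but no equation (2) appears. Section VI.B says Table 10 shows the first stage for this model. Its notes describe "Control means and first stage estimates of the impact of TREATMENT on alternate definitions of PARTICIPATION", and it gives one coefficient per participation measure.

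**The concern.** A variable that enters the first stage but not the outcome equation is an excluded instrument. As printed there are three: TREATMENT, TIME_WORKED and their product. Only the first was randomized. The second is post-randomization behavior that equation (1) allows to affect the outcome directly and that the plan also treats as an outcome.

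Most of the damage comes through the product term. Controls complete almost no modules (mean 0.01, Table 10 Panel A), so fitted participation is close to TREATMENT × (a + b·TIME_WORKED). That quantity is correlated with the TIME_WORKED main effect missing from (3). Deleting TIME_WORKED from (4) alone would therefore not repair the model.

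At stake are the employee-level 2SLS columns of Tables 3–6. For outcomes tied to hours, they would partly measure who stayed and worked more.

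**Working it through.** The plan gives no LATE estimate or power figure to reproduce. Input checks agree with its tables: 41,376 + 7,288 = 48,664 and 13,000 + 2,344 = 15,344 (Table 10); 2,071/7,288 = 28.4% (Table 7).

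**Formula.** Let W be the hours measure, p the treated fraction, m the mean modules among the treated, b the modules gained per unit of W, and g the outcome gradient on W. With no program effect, the estimate under (3)/(4) tends to

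g · Cov(P̂, W) / Var(P̂) = g · p·b·Var(W) / [p(1−p)m² + p·b²·Var(W)].

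**Assumption.** The documents give no gradient on hours. Two proxies are used: tenure days (SD 399.87, Table 3) and the stable/non-stable split.

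**Inputs, by subtraction from Tables 3, 7, 8 and 10**
- Non-stable control absenteeism: (41,376×2.23 − 13,000×3.39)/28,376 = 1.70%.
- Non-stable control tenure: (41,376×416.69 − 13,000×786.57)/28,376 = 247.2 days, a gap of 786.57 − 247.2 = 539.3 days.
- g = (3.39 − 1.70)/539.3 = 0.00314 points per day.
- Treated modules: stable 2.56 + 0.02 = 2.58; non-stable (7,288×1.17 − 2,344×2.58)/4,944 = 0.50. Hence b = 0.00385 per day.
- p = 7,288/48,664 = 0.150; m = 1.17.

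**Days proxy**
- Var(P̂) = 0.150×0.850×1.17² + 0.150×(0.00385×399.87)² = 0.530.
- Absenteeism: 0.150×0.00314×0.00385×399.87²/0.530 = 0.55 points per module.
- Tenure (g = 1): 174 days per module.

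**Split proxy**
- q = 13,000/41,376, so q(1−q) = 0.215 replaces Var(W), with group differences in place of slopes.
- Absenteeism 0.36 points and tenure 115 days per module.

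A separate derivation using the Table 10 coefficients (1.12 and 2.56) gave 0.56 points and 178 days under the days proxy.

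**Allowing for X.** If X absorbs a share of the gradient, the absenteeism bias shrinks in proportion: 0.18–0.27 with half left, 0.04–0.06 with 10% left, 0 with none left.

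**Stably employed, tenure.** p = 2,344/15,344, SD 376.96, m = 2.58, and b = 2.58/786.57 or half of that, give 65 or 39 days per module.

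**Other outcomes before X, same method**
- Recommended tests: 1.2–1.8 points (mean 58.0).
- Medical spending: −$11 to −$36, under 1% of $4,801 and about 0.1–0.2 of an unclustered SE of about $160. The days version assumes an SD of 380–400.
- BMI 0.05–0.08; exercise 0.2 points.
- Cholesterol 1.0–1.6 mg/dl and systolic pressure about 0.48 mmHg (split proxy). These are small against their means, but the split-proxy values are each about 3 unclustered SEs.

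**Simulated rejection of a true null for absenteeism at 5%** (25 of 160 sites treated in A and B):

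| Gradient left after X | A: ICC 0.02 (assumed) | B: ICC about 0.003 (assumed) | C: no other covariates |
|---|---|---|---|
| 100% | 100% | 100% | 100% |
| 25% | 97–100% | 100% | 88% |
| 10% | 37–46% | 92% | 32% |
| none | 5–10% | 6% | not run |
| TIME_WORKED added to (3), all rows run | 4–9% | 6–8% | 7–10% |

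In B the mean false estimate was 0.43, 0.11 and 0.04 points per module with 100%, 25% and 10% left. With TIME_WORKED in (3) it was −0.001 to 0.002. The gradient is an input to these simulations, so they show how sensitive the model is, not what the trial's gradient is.

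**The case against.** The strongest reply is that this is a drafting slip. The plan calls the model parallel to the ITT, never claims hours as an instrument, and defends exclusion only for site assignment. That may well be so, but nothing in the document restores the term, and the table notes cite an equation that is not there. A plan written to prevent specification searching should not leave this open.

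Several narrower points stand.

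- The control lists in the table notes prove nothing either way, because they also cover column 2, where equation (1) certainly contains TIME_WORKED. The list of X is introduced as non-exhaustive. The finding rests on the equations themselves, which write TIME_WORKED outside X.
- Table 10's single coefficient could be an average-exposure summary, as section VI.A plans for the ITT.
- Stable and non-stable staff differ in age and job mix, which X contains. How much of the absenteeism gradient X absorbs is unknown, and the rejection rate at 10% left runs from 32% to 92% depending on set-up.
- Equations (8)/(9) and the worksite-level LATE are free of the flaw, so a discrepancy might show. But (8)/(9) are sensitivity analyses for comparison with phase 1 and would not correct the base columns.
- Adding TIME_WORKED to (3) conditions on a post-randomization variable. This is a real cost, and it has to be stated as an assumption.

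**Conclusion.** The concern holds. As printed, the base employee-level LATE is biased for any outcome that varies with hours worked given X, and this follows from the equations without any proxy. The sizes are illustrative and assume no program effect, with tenure or the stable/non-stable split standing in for hours.

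For tenure the link with hours is close to mechanical and the bias is large. For absenteeism it matters unless X absorbs nearly all of the gradient. For recommended tests it is moderate. Cholesterol and systolic pressure could be affected relative to their standard errors. For spending, BMI and exercise it is small, and where hours and outcome are unrelated given X it is nil. The ITT columns and worksite-level 2SLS do not have this flaw. It should be corrected before the LATE columns are produced.

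**What to change.** 1. Add TIME_WORKED to equation (3), so that only TREATMENT and TREATMENT × TIME_WORKED are excluded instruments. State that this assumes treatment does not change hours worked, and refer to the exit and tenure comparison in section VI.C as evidence on that.
2. When tenure or time worked is the outcome, TIME_WORKED cannot sensibly be a covariate. Use the treatment-only equations (8)/(9) as the LATE, with the balance weights of section V.B rather than the phase 1 exposure weights of section VI.F.
3. Have Table 10 report the first stage actually used: both instrument coefficients and their joint test.
4. Correct the citation of equation (2) in the notes to Tables 3–6.

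The cost is one term, some wording and a re-run of the first-stage table. In simulation A, standard errors rose about 7–8% when 10% or less of the gradient was left (0.034–0.038 against 0.032–0.035 at 10% left). The treatment-only model is nearly twice as imprecise there (0.064–0.065) and drops the exposure interaction, but it avoids conditioning on hours. The authors could reasonably make it the base model throughout if they doubt the assumption in step 1.
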